## SCHEMA

## 1. BACKGROUND

### 1.1 Pancreatic Cancer

Pancreatic cancer is the tenth most common malignancy in the United States, yet the fourth leading cause of cancer death with a five year overall survival of less than 5%. While surgery offers the only potentially curative treatment, only 15-20% of patients present with disease that is resectable, and in these patients the 5 year survival is at best 20%. The poor survival outcomes are due to a high rate of metastatic progression, underscoring the need for more effective systemic regimens. In addition, 30% of patients die with progressive local disease. Therefore strategies to identify this subset of patients and intensify local therapy may also improve survival outcomes.

Patients who are candidates for potential surgery have either resectable disease or borderline resectable disease. Resectable tumors have no arterial contact with the celiac axis (CA), superior mesenteric artery (SMA), or common hepatic artery (CHA), and no contact or less than 180 degrees of contact with the superior mesenteric vein (SMV) or portal vein (PV) with no vein contour irregularity. The category of borderline resectable pancreatic cancer (BRPC) was first described in 1999 to classify tumors that were between resectable and locally advanced unresectable disease, and could potentially benefit from pre-operative therapy for downstaging prior to attempted resection. Since then, the definition of BRPC has evolved, and is primarily determined by pancreas protocol contrast-enhanced CT imaging to assess the relationship of the tumor to the vasculature. While slight variations in the definition of BRPC exist, the NCCN guideline criteria provide an accepted consensus definition. According to these guidelines, borderline resectable tumors include tumors of the pancreatic head and uncinate process that contact the CHA without extension to the CA or hepatic artery bifurcation, or contact less than 180 degrees of the SMA; or tumors of the body or tail that contact less than 180 degrees of the CA; and tumors contacting greater than 180 degrees of the SMV or PV, or with contour irregularity or short segment thrombosis of the vein, but with venous reconstruction feasible.

The potential for a resection with positive margins is increased when immediate resection is attempted in patients with BRPC. In patients who undergo resection with microscopic (R1) or grossly positive margins (R2), survival rates are not improved over that of patients with locally advanced unresectable disease. Moreover, a high rate of metastatic progression suggests that micrometastatic disease is likely present at diagnosis in a large subset of patients. Therefore neoadjuvant therapy is beneficial in patients with BRPC to increase the likelihood of achieving a margin negative resection, provide early control of occult micrometastatic disease, and select those patients without systemic progression who would benefit from surgical resection.

### 1.2 Adjuvant Therapy

Currently the standard of care management of patients with resectable pancreatic cancer entails six months of adjuvant chemotherapy with gemcitabine, or 5-Fluorouracil (5-FU), or gemcitabine with capecitabine. The CONKO-001 trial demonstrated a survival benefit with the use of adjuvant gemcitabine versus observation (5-year overall survival of 21% vs. 9%, median survival 22.8 months vs. 20.2 months). In the ESPAC-3 trial, survival outcomes were comparable with adjuvant gemcitabine vs. 5-FU, with median survival reported at 23.6 vs. 23 months, respectively. Treatment-related adverse effects were significantly increased with adjuvant 5-FU vs. gemcitabine (14% vs. 7.5%), and therefore gemcitabine remains a standard adjuvant chemotherapy regimen. The ESPAC-4 trial was a large

randomized study that compared six months of adjuvant gemcitabine alone to gemcitabine with capecitabine. Results were recently presented at the 2016 ASCO annual meeting, and a significant survival benefit was demonstrated with the combination of gemcitabine and capecitabine compared to gemcitabine alone (median survival of 28 months vs. 25.5 months, and 5 year overall survival of 28.8 vs. 16.3%). Based on these results, gemcitabine with capecitabine can be considered the preferred adjuvant chemotherapy regimen.

The role of post-operative radiation remains unclear. The early GITSG 9173 trial demonstrated a survival benefit with adjuvant 5-FU based chemoradiation compared to observation (median overall survival of 20 vs. 11 months), though the radiation approach is now considered outdated, as it was delivered in a split course fashion with a planned two week break mid treatment. The subsequent ESPAC-1 trial was a 2x2 randomization comparing observation, chemotherapy alone with 5-FU/leucovorin, chemoradiation with 5-FU, and chemoradiation followed by maintenance chemotherapy. A survival detriment was demonstrated with adjuvant chemoradiation, but multiple criticisms of the study design and analysis have called into question these results. Recent large retrospective studies and an analysis of the National Cancer Database from our institution have demonstrated a survival benefit with adjuvant chemoradiation vs. observation or chemotherapy alone. Therefore the role of post-operative radiation remains controversial, and the current RTOG 0848 phase III trial is examining the benefit of delayed chemoradiation after 6 months of adjuvant gemcitabine, compared to gemcitabine alone.

### **1.3 Neoadjuvant Therapy**

Up to 25% of patients who undergo upfront surgery do not receive any adjuvant therapy due to post-operative complications or early metastatic progression. Therefore, chemotherapy and/or radiation delivered in the pre-operative setting offers several advantages, particularly for patients with BRPC, foremost being the potential for downstaging to maximize the rate of margin negative resections. Additional advantages include early systemic therapy to address potential micrometastatic disease, and selecting those patients without early distant progression in whom surgical resection is beneficial.

Neoadjuvant therapy has not been compared to adjuvant therapy in a phase III trial, but multiple phase II and retrospective series have demonstrated promising outcomes. Prospective phase II studies have primarily focused on patients with resectable tumors, demonstrating the safety and feasibility of pre-operative gemcitabine-based chemotherapy with or without chemoradiation in these patients.

Data specific to patients with BRPC is more limited. In a retrospective series from MD Anderson Cancer Center, 160 patients with BRPC were identified of which 125 completed pre-operative therapy consisting of 2 to 4 months of gemcitabine-based chemotherapy followed by chemoradiation to 50.4 Gy in 28 fractions or 30 Gy in 10 fractions with concurrent 5-FU, paclitaxel, gemcitabine or capecitabine. 41% of patients were able to undergo resection after completing neoadjuvant therapy, and R0 resections were achieved in 94% of these patients. Survival was significantly prolonged in those patients who underwent resection (median overall survival of 40 months vs. 18 months for the cohort overall), which emphasizes the meaningful survival benefit associated with conversion to resectable disease. Preliminary results from the multi-institutional Alliance Trial A021101 were presented at the 2015 ASCO annual meeting. In this study, 22 patients with BRPC were treated with 4 cycles of mFOLFIRINOX chemotherapy (oxaliplatin 85 mg/m^2, irinotecan 180 mg/m^2, leucovorin 400 mg/m^2 on day 1 followed by 5-FU 2400 mg/m^2 x 48 hours) followed by chemoradiation to 50.4 Gy in 28 fractions with concurrent

capecitabine (825mg/m^2 twice daily). 15 patients (68%) underwent subsequent resection, while 7 patients had disease progression and 1 refused surgery. R0 resections were achieved in 14 of these 15 patients. Treatment-related toxicities were manageable, and the high rate of R0 resections supports the efficacy of pre-operative chemotherapy and chemoradiation in BRPC. These studies report promising rates of R0 resection after neoadjuvant therapy (41-64%), though the optimal sequence and combination of neoadjuvant therapy has not been well defined.

#### 1.4 Advances in Chemotherapy

Though gemcitabine with or without capecitabine, or 5-FU are still considered the standard adjuvant chemotherapy options, FOLFIRINOX (oxaliplatin 85 mg/m^2 over 2 hrs, followed by irinotecan 180 mg/m^2 over 90 min and leucovorin 400 mg/m^2 over 2 hrs, followed by 5-fluorouracil 400 mg/m^2 bolus and 2,400 mg/m^2 46 hrs continuous infusion) has proven to be a superior regimen in the setting of metastatic pancreatic cancer. In the randomized phase III PRODIGE4/ACCORD 11 trial comparing FOLFIRINOX with gemcitabine in patients with metastatic disease, overall survival was significantly improved from a median of 6.8 months with gemcitabine to 11.1 months with FOLFIRINOX. Progression-free survival (PFS) was improved from 3.3 months to 6.4 months, and response rates increased from 9.4% to 31.6% with FOLFIRINOX. Moreover, improvements in quality-of-life measures were reported with FOLFIRINOX compared to gemcitabine. Despite these results, there has been reluctance to adopt the widespread use of full dose FOLFIRINOX due to significant increases in grade 3-4 toxicities, specifically neutropenia, fatigue, diarrhea, and vomiting.

Retrospective studies have evaluated the efficacy and tolerability of FOLFIRINOX administered with dose modifications, including a retrospective analysis of patients with advanced pancreatic cancer treated at our institution with FOLFIRINOX between June 2010 and July 2011. The majority of the 35 patients analyzed received modest dose attenuations of irinotecan and/or 5-FU. These dose modifications resulted in improved tolerability with reduced rates of grade 3-4 toxicities, while maintaining comparable efficacy to that reported by Conroy et. al. Therefore a phase II study was completed in patients with locally advanced pancreatic cancer (LAPC) and metastatic pancreatic cancer (MPC) to evaluate a modified FOLFIRINOX regimen with upfront 25% dose reductions of the 5-FU bolus and irinotecan and routine use of pegfilgrastim. 31 patients with LAPC and 44 patients with MPC were enrolled. Rates of grade 3-4 adverse effects, including neutropenia, fatigue, and vomiting were significantly reduced compared to rates reported in the phase III trial. For MPC, the response rate was 35.1% and median overall survival was 10.2 months, consistent with comparable efficacy to full dose FOLFIRINOX. Results in patients with LAPC highlight the superiority of FOLFIRINOX compared to historical results with gemcitabine-based regimens. Median PFS and OS were prolonged at 17.8 months and 26.6 months, respectively. In comparison, median OS was just 15.2 months for patients without disease progression after induction gemcitabine plus or minus erlotinib who went on to receive chemoradiation in the recently published LAP07 randomized trial. Of the 31 patients with LAPC treated with modified FOLFIRINOX in our institutional trial, 13 patients (41.9%) underwent R0 resections. 6 of these patients received chemoradiation prior to surgery. Similar promising outcomes with the use of FOLFIRINOX in the locally advanced setting have been reported in multiple retrospective series.

Based on this institutional experience, a prospective phase II study is ongoing evaluating peri-operative modified FOLFIRINOX in patients with resectable pancreatic cancer.

## 1.5 Advances in Radiation Therapy

Studies evaluating the role of radiation therapy in the treatment of locally advanced pancreatic cancer have shown conflicting results. The ECOG 4201 study showed a modest but significant survival benefit with gemcitabine and concurrent radiation compared to gemcitabine alone (median overall survival of 11 months vs. 9.2 months, respectively). Retrospective and phase II studies have shown a further survival benefit when chemoradiation is employed after a period of induction chemotherapy, thereby excluding those patients with early distant failure. In the GERCOR combined analysis, patients received a minimum of 3 months of induction 5-FU or gemcitabine-based chemotherapy. Median overall survival was 15.0 months in those patients who went on to chemoradiation compared to 11.7 months with continued chemotherapy alone. In contrast, the recently published LAP-07 trial demonstrated no improvement in overall survival with chemoradiation to 54 Gy with concurrent capecitabine compared to continued chemotherapy after 4 months of induction gemcitabine or gemcitabine plus erlotinib. The addition of chemoradiation did prolong the time to second-line therapy, and provide a local tumor control benefit. Despite the conflicting results in these studies regarding the benefit of chemoradiation, the median overall survival after gemcitabine-based chemotherapy followed by chemoradiation ranged from 11 – 15.2 months and appears inferior to survival outcomes for patients with LAPC treated with FOLFIRINOX, where median overall survival reaches 26.6 months in our prospective institutional study. This comparison emphasizes the importance of effective systemic therapy prior to chemoradiation. The efficacy of upfront FOLFIRINOX to control micrometastatic disease is likely critical to achieve the optimal benefit from local therapy. Therefore in the era of FOLFIRINOX, radiation therapy may have a greater impact on survival outcomes.

Conventional radiation entails daily treatments to a dose of 50.4 – 54 Gy in 1.8 to 2 Gy fractions over the course of five to six weeks using three-dimensional conformal techniques (3D-CRT) or intensity-modulated radiation therapy (IMRT). Consensus guidelines recommend treating the gross tumor volume with 1.5 – 2 cm expansions in the anterior, posterior, and lateral dimensions, and 2 – 3 cm expansions craniocaudally to take into account microscopic disease extension, motion of the tumor with respiration, and daily set-up variation. The volume of irradiated adjacent normal tissue (duodenum and stomach), in part due to the rather generous margins employed around the tumor volume, limits the radiation dose that can be safely delivered. IMRT is a technique that relies on a computer-aided optimization process to generate a treatment plan in which the intensity of multiple radiation beams is varied across the treatment field in order to conform the radiation dose to the tumor target and reduce dose to neighboring normal structures. A recent retrospective study demonstrated reduced rates of acute grade 2 or higher gastrointestinal toxicities when IMRT vs. 3D-CRT was employed for definitive chemoradiation in patients with LAPC, suggesting that IMRT may allow for safe escalation of the radiation dose to the tumor using conventionally fractionated radiation.

Stereotactic body radiotherapy (SBRT) is an emerging treatment option for patients with pancreatic cancer, in which highly focal radiation is delivered to the tumor most often with IMRT planning, allowing for dose escalation which may enhance local tumor control compared to conventional radiation. SBRT relies on methods to account for motion of the tumor target with respiration, including obtaining a 4-dimensional planning CT scan to visualize motion of the tumor, and respiratory gating for treatment only in pre-specified phases of the respiratory cycle or abdominal compression to reduce respiratory motion during treatment. Gold fiducial markers are placed in the tumor or surrounding pancreas to precisely align the pancreas on the day of treatment. These techniques allow for the delivery of highly conformal ablative doses of radiation in 5 or fewer treatments.

Multiple phase I-II single institution studies have evaluated the use of SBRT for LAPC. Early studies from Stanford University explored single fraction treatment alone, as a boost after conventionally fractionated radiation, or in combination with sequential gemcitabine. While high rates of local control were reported at 1 year (94 – 100%), this was at the cost of increased grade 2 or higher acute GI toxicities (12.5 – 19%), and significant grade 2 or higher late GI toxicities (20-44%) including duodenal ulcers, and less commonly stenosis or perforation. Subsequent studies utilized a multi-fraction approach (typically 3 to 5 treatments), and maintained effective local control (78 – 85% at 1 year) with reduced GI toxicities. A recent phase II multi-institutional study evaluated gemcitabine followed by fractionated SBRT. Patients received up to 3 weeks of gemcitabine (1000 mg/m^2) followed one week later by SBRT to 33 Gy in 5 fractions delivered over 1 to 2 weeks, and gemcitabine until disease progression or toxicity. The primary endpoint was late grade 2 or higher GI toxicities compared to historical controls. When compared to prior studies using single-fraction SBRT, GI toxicities were reduced to 2% grade 2 or higher acute toxicity, and 11% grade 2 or higher late toxicity. The median overall survival was 13.9 months. Local control at 1 year was 78% which compares favorably to historical controls treated with conventionally fractionated radiation, such as the recently published LAP-07 trial. Therefore advantages of SBRT include the fact that the biologic effect of larger radiation fractions may provide a therapeutic benefit with improved local control compared to conventionally dosed radiation, and the shorter treatment course can be more easily integrated with other treatment modalities with less time off of effective multi-agent chemotherapy.

Given these promising local control outcomes, SBRT may also increase the rate of conversion to resectable disease for patients with BRPC or LAPC. While SBRT in the neoadjuvant setting has not been prospectively evaluated, a single institution retrospective experience from Moffitt Cancer Center reported on the safety and efficacy of pre-operative SBRT. Patients with LAPC or BRPC received induction chemotherapy (most commonly gemcitabine, taxotere, and capecitabine) followed by SBRT in 5 fractions. The tumor was treated to 25-30 Gy, and the region of tumor abutting vessels received a higher dose (35-50 Gy). Treatment was well tolerated, with no acute grade 3 or higher toxicities reported, and only 5.3% late grade 3 or higher toxicities. Rates of surgical complications were acceptably low. 54% (31/57) of BRPC patients underwent an R0 resection after neoadjuvant therapy, and the median overall survival was 16.4 months. Updated results included a larger number of patients (n=23) receiving induction FOLFIRINOX. In this small retrospective experience, the combination of induction FOLFIRINOX and SBRT as neoadjuvant therapy was well tolerated. Most patients receiving FOLFIRINOX had LAPC, and R0 resection rates were significantly higher in FOLFIRINOX recipients versus other induction chemotherapy regimens (5 of 21 vs. 0 of 28, p = 0.011). Finally, retrospective data from Johns Hopkins University presented in abstract form compared R0 resection rates for BRPC or LAPC patients receiving neoadjuvant chemotherapy alone or induction chemotherapy followed by SBRT. Rates of R0 resection were significantly higher in patients who received SBRT compared to those who received chemotherapy alone (87.2 vs. 48.6%). Taken together, these single institution retrospective studies demonstrate the tolerability of neoadjuvant SBRT and report increased rates of R0 resections particularly for BRPC that warrants further evaluation in a prospective trial.

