### 2.2 Secondary Objectives

- 2.2.1 To evaluate the radiographic response to neoadjuvant therapy by comparing IV contrast CT scans before and after therapy.
- 2.2.2 To evaluate the pathologic response to neoadjuvant chemotherapy and stereotactic radiation.
- 2.2.3 To determine rates of recurrence (local only, systemic only, and both local and systemic), progression free survival, and overall survival.
- 2.2.4 To determine rates of grade 3 or greater gastrointestinal toxicity, including acute toxicities occurring within 3 months of treatment, and late toxicities occurring over 3 months after completion of radiation.

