### **4.3 Radiation-Specific Safety Guidelines**

The radiation fractionation scheme proposed in this study (33 Gy in 5 fractions) was evaluated in a prospective multi-institutional phase II study in which patients with locally advanced pancreatic cancer received gemcitabine followed by SBRT. The rate of grade 3 or higher acute GI toxicity was 2% and the rate of grade 3 or higher late GI toxicity was 8%. Based upon this study and other published studies evaluating multi-fraction SBRT for pancreatic cancer, a rate of grade 3 GI toxicity of 20% or higher would be unexpected. An interim safety analysis will be performed by the PI after 5 patients complete 3 months of follow-up after SBRT. Study accrual will continue during this time period. If the rate of grade 3 GI toxicity that is probably related to SBRT exceeds 20%, then accrual will be held and the protocol and consent will be revised.

Refer to section 7 for recommendations for the management of toxicities related to SBRT.

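### The 20% SBRT accrual-hold limit is justified with acute and late GI toxicity but read only once, from 3 months after SBRT, so it rests mainly on acute data

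*Combined protocol and SAP*

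**What the plan says.** Section 4.3 takes its benchmark from a multi-institutional phase II study of 33 Gy in 5 fractions in locally advanced disease: "The rate of grade 3 or higher acute GI toxicity was 2% and the rate of grade 3 or higher late GI toxicity was 8" (per cent). From this and similar studies it concludes that a grade 3 GI rate of 20% or more would be unexpected. The check is a single look: "An interim safety analysis will be performed by the PI after 5 patients complete 3 months of follow-up after SBRT". Accrual goes on meanwhile. The consequence is: "If the rate of grade 3 GI toxicity that is probably related to SBRT exceeds 20%, then accrual will be held", with revision of protocol and consent.

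Objective 2.2.4 divides toxicity in time: "acute toxicities occurring within 3 months of treatment, and late toxicities occurring over 3 months after completion of radiation".

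Section 1.5 gives two further figures. For the same phase II study, "GI toxicities were reduced to 2% grade 2 or higher acute toxicity, and 11% grade 2 or higher late toxicity". For a retrospective pre-operative SBRT series, "no acute grade 3 or higher toxicities reported, and only 5.3% late grade 3 or higher toxicities".

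Section 15 adds a DSMC safety analysis after 10 patients are enrolled (enrolment suspended until the DSMC approves), safety submissions to the DSMC at least yearly, and a general power to amend or suspend. None of these has a toxicity limit or a follow-up requirement. Section 14.2 captures new adverse events to 30 days after last treatment unless otherwise specified. After that it names only unexpected serious events attributed to drug administration.

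**The concern.** The benchmark and the reading cover different periods. The limit is argued from acute and late rates together, but it is read when the fifth patient reaches the boundary between the two periods. Most of the serious GI toxicity in the cited study lies beyond that boundary.

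Two things are at stake. An excess of late GI toxicity well above the protocol's own limit would usually not trigger the one rule that has a number. And a clean result at the look could be taken as support for the 20% limit in general, when it speaks mainly to the acute period. Reading more patients at 3 months would not cure this, because the gap is in follow-up time.

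**Working it through.** The plan states no error rate or detection probability for this rule, so there is no figure of its own to reproduce.

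**Late share of the cited toxicity**
- Phase II study, grade 3 or higher GI (4.3): 8/(2+8) = 80%. If every acute case was also a late case, the total is 8% and 6/8 = 75% is late only.
- Same study, grade 2 or higher GI (1.5): 11/(2+11) = 85%. This is not independent evidence.
- Retrospective pre-operative series (1.5): 5.3/(0+5.3) = 100%, at other doses and not labelled GI. I do not rely on it.

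**What triggers a hold**
1/5 = 20% does not exceed 20%, so at least 2 of 5 are needed.

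**Follow-up at the look**
The documents give two accrual paces: 28 patients in two years (Section 12), or 24/28 = 0.86 months apart; and about 6 a year (Section 3.4), or 2 months apart. When the fifth patient reaches 3 months, the five have 3 to 6.4 months or 3 to 11 months of follow-up.

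**Probability of a hold**
Assumptions: true cumulative grade 3 or higher rate 30%, split 20:80 (6% acute, 24% late); late events spread evenly over L months from month 3; even spacing; no dropout. Patient i (i = 0 to 4, latest to earliest) has had an event with probability

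p_i = 0.06 + 0.24 × min(1, i × spacing / L).

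Example with spacing 2 and L = 12: p = 0.06, 0.10, 0.14, 0.18, 0.22. P(0 events) = 0.94 × 0.90 × 0.86 × 0.82 × 0.78 = 0.465. P(1 event) = 0.465 × 0.839 (the sum of p/(1−p)) = 0.391. P(hold) = 1 − 0.465 − 0.391 = 0.144.

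| Spread of late events, L | 28 in two years | 6 a year |
|---|---|---|
| 3 months | 24% | 34% |
| 6 months | 12% | 27% |
| 12 months | 7% | 14% |
| 21 months | 5% | 9% |

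With full late follow-up of the same five: 1 − 0.7^5 − 5 × 0.3 × 0.7^4 = 1 − 0.168 − 0.360 = 47%. With a 75% late share and L = 12 the two entries are 9% and 16%. At the cited 10% cumulative rate (2% and 8%, L = 12) they are 1% and 2%, against 8% with full follow-up.

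**Does the DSMC review after 10 enrolled fill the gap?**
Assume 5 months from enrolment to the end of SBRT (eight 2-week cycles, then SBRT). At 0.86-month spacing the tenth patient enrols at month 9 × 0.86 = 7.7. The first is then 2.7 months past SBRT, so nobody is beyond 3 months. At 2-month spacing the tenth enrols at month 18, and five or six patients have reached 3 months, but the review has no limit to apply.

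**The case against.** A reader might infer that the rule counts only acute events, or is blind to late ones. The text does not say so. It counts grade 3 GI toxicity without a time restriction, 3 months is a minimum, and earlier patients bring some late follow-up. The table credits this.

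A reader might also infer that 80% to 100% of the relevant toxicity is late. Only the 80% figure (or 75%) is GI-specific and uses this fractionation. It comes from locally advanced disease, whereas resectable patients here have surgery 4 to 12 weeks after SBRT. Carrying the split over is an assumption.

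Nor do the documents support saying that a late excess would go unreviewed while accrual simply continued. Enrolment stops at 10 patients until the DSMC approves, yearly submissions follow, events more frequent than expected go to expedited reporting, and the PI or DSMC may suspend. For resected patients, event capture can run about 8 months past SBRT: up to 12 weeks to surgery, up to 12 to adjuvant start, 8 of chemotherapy, then 30 days. What these safeguards lack is a number and a required length of follow-up.

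The timing of late events is not given, and short spreads narrow the gap (24% or 34% against 47%). Five patients are few in any case: with full follow-up the rule would still miss a 30% rate more than half the time. An early look for acute harm is a reasonable choice, and nothing here argues for dropping it.

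**Conclusion.** The point holds as a mismatch between the basis of the limit and the moment it is read. Section 4.3 draws on acute and late rates, yet the only numeric trial-level toxicity limit is applied once, mainly to acute data. At a true 30% rate the probability of a hold is 7% or 14% with late events over 12 months, and 5% to 34% across spreads of 21 down to 3 months, against 47% with full late follow-up. This rests on the assumed 30% rate, the 20:80 split carried over from locally advanced disease, evenly spread late events, even accrual and no dropout. The direction is the same throughout the table; the size depends on timing that the documents do not give. It should be corrected, but it does not show that late toxicity is unmonitored.

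**What to change.** 1. In 4.3, keep the 3-month look and state that it mainly addresses acute toxicity.
2. In 4.3 and 15, also apply the existing limit (a rate above 20%) to cumulative acute plus late grade 3 or higher GI toxicity probably related to SBRT, at the DSMC submissions already required. Start once a stated minimum of SBRT-treated patients, for example 10, are past 3 months, so that one event in a handful of patients cannot trigger a hold.
3. State that late SBRT GI events are collected for this purpose beyond the 30-day window of 14.2. Objective 2.2.4 needs them anyway, and the calendar marks no toxicity assessment in post-treatment follow-up.

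The cost is a few sentences, one table in a report already due, and a somewhat higher chance of a hold at the cited rates. In simulation (5-month lead-in, no dropout, late events over 12 months, yearly submissions, minimum of 10), the overall hold probability is about 5% to 6% at a 10% cumulative rate, against 1% to 2% now. At 30% it rises to about 62% (two-year accrual) or just over 70% (6 a year). With a minimum of only 5 at 6 a year, the chance at the 10% rate would be about 14%.

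One limit on the benefit: under two-year accrual the first yearly submission with 10 such patients is at month 24, after the last enrolment (27 × 0.86 = month 23.1), so a hold on accrual would come too late. The tenth patient passes 3 months at about month 5 + 3 + 9 × 0.86 = 15.7. Section 15 lets the DSMC ask for submissions more often than yearly, and one near that point would fall within accrual. By then less late follow-up exists, and the simulated hold probability at 30%, counting both looks, is about 18%.
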